### **3. Sample size:**

This prospective, double-arm, single-blind, multicenter randomized controlled trial evaluated the effectiveness of RISE anastomosis with ileocecal valve reconstruction. The postoperative stool formation time served as the primary endpoint for sample size calculation. Based on our prior trial results, the stool formation rate was approximately 65% in the RISE group and 33.3% in the control group on day 2 postoperatively. With a two-tailed test level  $\alpha=0.05$  and a 1:1 group ratio, PASS11.0 software estimated minimum sample sizes of 85 cases per group. Considering a 10% dropout rate, each group required 94 additional cases ( $85 + 85 \times 10\%$ ), totaling 188 cases combined. The study employed block randomization with minimum blocks of 4 samples. Subsequently, sample allocation was determined based on regional average patient intake levels to match block sizes.

According to the number of patients with right-sided colon cancer admitted by each center per year, the number of cases was allocated proportionally among the research centers,

Table 1 Sample size allocation of each sub-center

Center units	Sample size allocation
Second Affiliated Hospital of Army Military Medical University	108
The First Affiliated Hospital of Chongqing Medical University	20
Affiliated Hospital of North Sichuan Medical College	20
Guangan People's Hospital, Sichuan Province	20
Third People's Hospital of Yibin City, Sichuan Province	20

[figure not shown]

Figure 1 PASS11.0 software interface-sample size calculation results

#### **4. Research process**

The research process is divided into screening period, treatment period and follow-up period, the details of which are as follows:

##### **1. Screening period**

Time point: preoperative

## 2. Treatment

Time node: from intraoperative to 7 days after surgery

Research content and items to be collected/detected:

(1) Operation implementation:

In this study, the intervention group and the control group only differ in the digestive tract reconstruction method:

a. RISE anastomosis group (intervention group)

All procedures were performed under general anesthesia with the patient in lithotomy position. In accordance with established principles of laparoscopic right hemicolectomy, five cannulation needles were inserted to facilitate D2 lymph node dissection from inside out.

Step 1: Measurement and Dissection: Mark a 2 cm mark along the mesocolon at the terminal transverse colon, and mark the ileal distal end approximately 10 cm and 12 cm from the ileocecal junction. Use an endoscopic linear stapler to dissect the right half of the transverse colon. Perform mesenteric trimming on the ileal distal segment, ligate the ileum at marked points with 4-0 silk sutures, then dissect it using an ultrasonic scalpel. Carefully inspect both ends and disinfect with alcohol swabs.

Step 2: Intestinal End Inversion and Colon Insertion: Using an ultrasonic scalpel, make a horizontal incision 2 cm from the colon's distal end. Divide the proximal ileum into three equal segments, then suture them to the muscularis **浆膜** layer with 3-0 silk sutures, creating a 1.5 cm mucosal flap to form a simulated ileocecal valve. Perform an interrupted suture of three stitches at the midpoint of the inverted ileal segment using 3-0 silk sutures. Insert the intact ileal segment into the colon without

torsion, ensuring adjacent mesenteric vessels are free from torsion and tension.

**Step 3: Intestinal Colon End-to-End Anastomosis.** When there is no intestinal volvulus, fix three sutures at the transverse colon opening, one-third of the distance from the mid-point of the small bowel eversion line, to ensure precise fixation of the small intestine on the transverse colon. Close the anastomosis with 3-0 catgut suture (with barbs) using a tight stitch. If the closure is inadequate, perform interrupted suturing. After confirming no significant fistula formation, encase the anastomosis with seromuscular layer. Continuously suture the gap between the ileum and colonic mesentery with 3-0 catgut suture (with barbs). Finally, manually assess the anastomosis's size and patency.

[figure not shown]

Figure 2 Schematic of RISE anastomosis steps. A-B: Identify and mark the transection sites on the transverse colon stump and terminal ileum. C-D: Evert the terminal ileum to mimic the anatomical structure of the ileocecal valve. E-F: Place fixation sutures at the transverse colon opening. G-H: Complete the RISE anastomosis of the terminal ileum with colon.

b. Conventional lateral side anastomosis group (control group)

After inserting the same cannula, ligating blood vessels, and making a 10 cm distal transection at the transverse colon mass along with a 15 cm proximal transection at the ileocecal valve, the specimen was extracted through a small midline incision. A linear stapler was used in vitro for the side-to-side ileocolonic anastomosis, followed by closure of the common intestinal incision with a second stapler. The anastomotic site was reinforced with 3-0 catgut sutures using reverse-staple technique.

(2) Intraoperative index recording:

- Total operation time (min);
- Surgical duration of anastomosis (min);
- Blood loss during operation (mL);
- Blood transfusion volume (mL);
- 

(3) Immediate postoperative monitoring:

- Blood pressure, heart rate, respiration and body temperature at 24h, 48h and 72h after surgery;
- Daily postoperative physical examination (abdominal signs, resumption of bowel sounds);
- Bristol stool score (recorded daily for 7 consecutive days);

(4) Laboratory test:

Blood routine and blood biochemistry (monitoring inflammatory indicators and metabolic status) at 24h and 72h after surgery;

(5) Postoperative complication records (according to Clavien-Dindo grading system):

Table 1. Clavien-Dindo grading system for surgical complications

I	
 
① Abnormal conditions that do not require medication or surgery, endoscopy and radiation therapy.
 
② Antispasmodic, antipyretic, analgesic, diuretic, electrolyte and other drug therapy and physical therapy.
 
③ Open infected wounds at the bedside
 

II	
 
① Complications requiring the use of medications other than those described above for treatment of grade I complications.
 
② Blood transfusion, total parenteral nutrition
 

III	Complications requiring surgery, endoscopy or radiation therapy
IIIa	No general anesthesia is required
IIIb	Need general anesthesia
IV	Life-threatening complications (including central nervous system complications, such as cerebral hemorrhage, ischemic stroke, subarachnoid hemorrhage, but not transient)

	ischemic attack) require IC/ICU management
IVa	Single organ dysfunction (including dialysis)
IVb	Multiple organ dysfunction
V	die
"d"	If a patient has complications at discharge (see example in Table 2), the corresponding complication grade should be followed by the suffix "d". This label indicates that follow-up is required to fully assess the complication.

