## I. RESEARCH CONTEXT

Colorectal cancer, a prevalent tumor in the digestive tract, has shown an increasing incidence rate year by year. Laparoscopic right hemicolectomy serves as the standard surgical approach for tumors involving the ascending colon, cecum, and partial transverse colon, with its conventional resection scope encompassing portions of the ileum, ileocecal valve, cecum, ascending colon, and transverse colon [1]. The ileocecal valve—a semilunar fold formed by thickened muscular tissue and mucosal lining at the terminal ileum's junction with the cecum—functions as a sphincter-like structure that separates the small intestine from the large intestine. This anatomical feature plays a crucial role in regulating nutrient absorption through intestinal contents [2-3]. However, current right hemicolectomy procedures routinely omit ileocecal valve preservation, neglecting this critical physiological structure. This omission may lead to two major complications: (1) Loss of the ileocecal valve's "gate mechanism": As a bidirectional valve, the ileocecal valve restricts intestinal contents from rapidly flowing into the cecum, thereby maintaining nutrient absorption efficiency. Valve absence allows excessive intestinal contents to enter the colon, disrupting bile acid reabsorption and potentially causing both bile acid malabsorption (BAM) and bile acid diarrhea (BAD)[4]. (2) Disruption of the ileocecal valve's "anti-reflux defense": When colonic bacteria infiltrate the ileum and proximal small intestine, they compromise the intestinal microbiota barrier, triggering severe bacterial overgrowth (SIBO). This condition frequently causes recurrent abdominal bloating, diarrhea, and other chronic gastrointestinal symptoms. In severe cases, it may impair nutrient absorption including vitamin B12 and fatty acid processing – a common complication in right hemicolectomy patients that significantly compromises postoperative recovery outcomes[5].

According to the existing research, there are two ways to preserve the function of the ileocecal valve: one is to reduce the scope of surgical resection and directly retain the ileocecal valve; the other is to reconstruct the corresponding function after the removal of the ileocecal valve as far as possible. However, there are the following

problems in clinical application:

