## **II. RESEARCH OBJECTIVES**

### **1. Main objectives:**

To evaluate the efficacy of total laparoscopic/robot-assisted right hemicolectomy combined with ileocolonic RISE anastomosis (intervention) in improving postoperative stool formation time (primary outcome) in patients with right hemicolectomy for colorectal cancer compared with traditional side-to-side

anastomosis.

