## **III. RESEARCH DESIGN**

### **1. Research on the overall design**

This prospective, single-blind, double-arm, multicenter, randomized controlled clinical trial with superiority design aims to compare postoperative intestinal function recovery between complete laparoscopic/robot-assisted right hemicolectomy combined with RISE anastomosis and traditional side-to-side anastomosis in patients with right-sided colon cancer. Eligible participants will be randomly assigned into RISE anastomosis and conventional anastomosis groups through zonal randomization, with evaluation of key outcomes including postoperative bowel function recovery (primary endpoint), complications, nutritional metabolism, quality of life, and oncological prognosis. Patients must provide informed consent prior to surgery, and all procedures are performed by senior physicians with extensive experience at each

center to ensure standardized protocols.

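### The arms are said to differ only in reconstruction, but the operative steps also remove about 3 to 5 cm more ileum from controls

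*Protocol*

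**What the plan says.** All references are to the Protocol, section III.4, 2. Treatment, item (1), unless stated otherwise.

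- **General claim.** The section opens by saying that "the intervention group and the control group only differ in the digestive tract reconstruction method".
- **RISE arm, Step 1, ileum.** The surgeon is told to "mark the ileal distal end approximately 10 cm and 12 cm from the ileocecal junction". The ileum is then tied at the marked points and divided. The text does not say which mark is the final cut.
- **RISE arm, Step 1, colon.** The instruction is "Use an endoscopic linear stapler to dissect the right half of the transverse colon". No distance from the tumour is given.
- **Control arm (b), both cuts.** The instruction is "making a 10 cm distal transection at the transverse colon mass along with a 15 cm proximal transection at the ileocecal valve".
- **Control arm (b), access.** After that, "the specimen was extracted through a small midline incision. A linear stapler was used in vitro for the side-to-side ileocolonic anastomosis".
- **Place of the RISE join.** The RISE steps do not state it. Section II.1 describes the intervention as "total laparoscopic/robot-assisted right hemicolectomy combined with ileocolonic RISE anastomosis (intervention", and section III.1 describes the comparison as "complete laparoscopic/robot-assisted right hemicolectomy combined with RISE anastomosis and traditional side-to-side anastomosis".

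The intraoperative record in item (2) lists operation time, anastomosis time, blood loss and transfusion volume. It does not list the length of bowel removed.

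**The concern.** A two-arm surgical trial can credit a difference to the reconstruction only if the resection before it is the same in both arms. Here the ileal resection is written differently for each arm, although the protocol says nothing but the reconstruction differs.

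The ileal cut is assigned together with the treatment. Randomisation therefore cannot balance it, and the centre-effect methods named in section V.7 deal with a different source of variation. A covariate for resected length would not rescue the comparison either: length would be almost determined by arm, and it is not on the list of items to be recorded.

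The outcomes are ones that the ileum could plausibly influence. The primary endpoint is time to first formed stool (section III.5), and the secondary endpoints include bile acid and vitamin B12. If removing more ileum worsens any of these, the excess falls on the control arm and flatters RISE.

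**Working it through.** **1. Are the two distances comparable?** One is measured from the ileocecal junction, the other from the ileocecal valve. Section I places the valve where the terminal ileum meets the cecum, so I treat the two as the same point. The protocol should nevertheless use one term.

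**2. Side by side.**

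| Step | RISE | Control | Same rule? |
|---|---|---|---|
| Ileal cut | marks at about 10 and 12 cm | 15 cm | No |
| Colonic cut | right half of transverse colon; no distance from tumour | 10 cm distal to tumour | Not shown either way |
| Place of join | not stated | outside the body | Not shown either way |

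Only the first row is a stated difference in resection.

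**3. Size of the ileal difference.**

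- Final RISE cut at 12 cm: 15 − 12 = 3 cm; 15/12 = 1.25, so 25% more in controls.
- Final RISE cut at 10 cm: 15 − 10 = 5 cm; 15/10 = 1.50, so 50% more in controls.
- Patients assigned the longer cut: 188/2 = 94 (section III.3).

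**4. What could it do to the result?** The documents give no effect of ileal length on stool form, so this step rests on assumed shifts. The other inputs come from section III.3: 85 evaluable patients per arm, a control day-2 formed-stool rate of 33.3%, a RISE rate of 65%, two-sided α = 0.05. The planned difference is 65 − 33.3 = 31.7 points.

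Suppose the valve does nothing and the ileal difference alone raises the RISE rate by *s*. The chance of a significant result favouring RISE is the sum of Bin(x; 85, 0.333 + s) × Bin(y; 85, 0.333) over all pairs (x, y) for which the pooled z statistic exceeds 1.96.

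| Assumed shift s | Chance of a significant result favouring RISE |
|---|---|
| 0 points | 2.4% |
| 2 points | 4.5% |
| 5 points | 9.8% |

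A 5-point shift is 5/31.7 = 16% of the planned difference.

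This uses the day-2 proportion because the sample size does. The primary endpoint is a time, so the figures indicate scale only. The documents allow no corresponding figure for bile acid or vitamin B12.

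**The case against.** The best defence has four parts.

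**The comparison is of whole operations.** Section II.1 names the entire RISE procedure as the intervention, and a conventional stapled control joined outside the body is a legitimate comparator. That is right as far as it goes, and there is no need to require joining inside the body in both arms. But it is not what the treatment section claims, and a package comparison does not need different ileal cuts.

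**The mechanism is not documented.** Section I speaks of "disrupting bile acid reabsorption and potentially causing both bile acid malabsorption (BAM) and bile acid diarrhea (BAD", but it attributes this to absence of the valve, not to length of ileum. Both arms lose the native valve and at least about 10 cm of ileum, so only the increment is in question. This stands: that the extra 3 to 5 cm affects stool form, bile acid or B12 is inference.

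**The RISE distances are approximate.** No tolerance is given, so achieved lengths may overlap between arms. This also stands. But both RISE marks fall short of 15 cm, no other section aligns them, and resected length is not listed for recording, so overlap could not be checked.

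**The other apparent differences are not established.** A reader might infer that the colonic margins differ. A missing number for RISE does not show that, and that arm is also told to follow established principles of right hemicolectomy. A reader might also infer that the control's join outside the body contradicts the *only differ* sentence. The place of joining can fairly be counted as part of the reconstruction, the RISE text does not state it, and the wording in section III.1 can be read as applying the complete laparoscopic approach to RISE alone. Both are matters to clarify, not contradictions.

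**Conclusion.** The point holds for the ileal cut. The protocol says that the arms differ only in reconstruction, and then assigns controls about 3 to 5 cm (25% to 50%) more ileal resection. The difference is fixed by arm and cannot be separated from the valve in the analysis. It may favour RISE on the primary endpoint and on bile acid and vitamin B12.

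It would be tempting to conclude that this could account for a positive trial. The documents do not support that. They give no effect size, and even an assumed 5-point shift is 16% of the planned difference and would give a significant result favouring RISE in about one trial in ten if the valve had no effect. A modest inflation of the RISE effect is plausible; production of the whole planned effect is unlikely.

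The verdict assumes that the ileocecal junction and valve mark the same point and that surgeons follow the distances as written. It should be corrected, mainly because correction is cheap and the present wording supports an attribution that the operative steps do not.

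**What to change.** 1. In section III.4, 2. Treatment, set **one ileal cut distance**, measured from the same named landmark, for both arms. For RISE, say which mark is the final cut and place the second mark relative to it.
2. Apply the control's colonic margin rule (10 cm distal to the tumour) to RISE as well.
3. Add length of ileum and length of colon removed to the intraoperative record in item (2).
4. State where the RISE join is made. If it differs from the control, delete *only* from the opening sentence and describe the comparison, there and in section II.1, as one of two operations.

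**Cost.** Items 1, 2 and 4 are text edits, and item 3 adds two measurements per operation. No extra patients are needed. Surgeons in one arm would shift their ileal cut by 3 to 5 cm. If item 4 leads to the two-operations wording, the conclusion is limited to the operations as packages.

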#### (6) Biological specimen collection:

biological specimen	Method of collection	Collection volume	use	Method of preservation
Organizing samples	Clinical additional collection	About 10g	Pathological analysis Molecular mechanism studies	Some were fixed in 10% formalin (for pathological analysis) and some were rapidly frozen in liquid nitrogen and transferred to -80 °C (for molecular mechanism studies)

### 3. Follow-up period

Time nodes: 1 month, 3 months, 6 months and 1 year after surgery

Research content and items to be collected/tested:

#### (1) 1 month ( $\pm$ 1 week) after surgery:

- Intestinal function evaluation: barium contrast (observation of intestinal passage time and anastomosis morphology);
- Colonoscopy (to assess mucosal healing and inflammation at the anastomosis).
- Laboratory tests: blood routine, blood biochemistry, serum vitamin B12 test, tumor markers (CEA, CA19-9);
- Imaging examination: chest X-ray, abdominal CT enhancement (to assess anastomosis healing and tumor recurrence);

- Human body composition analysis (assessment of patient nutrition);
- Quality of life assessment: EORTC QLQ-C30 and QLQ-CR29 scales;
- Collection of biological specimens:

biological specimen	Method of collection	Collection volume	use	Method of preservation
Blood samples	Clinical additional collection	Fasting venous blood 10mL	Subsequent metabolites and molecular mechanism analysis	Centrifuge and separate plasma/saliva for-80°C storage
Stool samples	Clinical additional collection	5g	Fungal profiling	After sterile collection, it was directly frozen and stored at-80°C

## (2) 3 months, 6 months and 1 year ( $\pm$ 1 week) after surgery:

- Laboratory tests: blood routine, blood biochemistry, serum vitamin B12 test; tumor markers (CEA, CA19-9);
- Imaging examination: chest X-ray, abdominal enhanced CT (to assess anastomosis healing and tumor recurrence);
- Human body composition analysis (assessment of patient nutrition);
- Collection of biological specimens:

biological specimen	Method of collection	Collection volume	use	Method of preservation
Blood samples	Clinical additional collection	Fasting venous blood 10mL	Subsequent metabolites and molecular mechanism analysis	Centrifuge and separate plasma/serum for-80°C storage
Stool samples	Clinical additional collection	5g	Fungal profiling	After sterile collection, it was directly frozen and stored at-80°C

Research process table

search procedure	Screening period	stage of therapy			follow-up period			
		Postoperative 24h	Postoperative 48h	Postoperative 72h	Postoperative 1 month	Postoperative 3 months	Postoperative 6 months	Postoperative 1 year
Sign the informed consent form	√							
Review selection/exclusion criteria	√							
General information	√							
medical history	√							
check-up	√	√	√	√				
vital sign	√	√	√	√				
Full abdominal scan with enhanced CT	√				√	√	√	√
Chest X-ray	√				√	√	√	√
routine blood test	√	√		√	√	√	√	√
Blood Biochemistry 1	√	√		√	√	√	√	√
Surgery time		√						
amount of bleeding		√						
mRS grade		√						
NIHSS grade		√						
Therapeutic medication		√	√	√				
complication		√	√	√	√	√	√	√
adverse event		√	√	√	√	√	√	√
enteroscopy					√			
Barium contrast					√			
Bristol Fecal Score	√	√	√	√	√	√	√	√
Stool samples	√				√	√	√	√
Blood samples	√				√	√	√	√
Organizing samples		√						
remarks :	1: Blood biochemistry includes liver function, kidney function, blood electrolyte, blood sugar, blood lipid							

## **5. End-point indicators**

Key endpoint indicator: Time to first stool formation post-surgery (Bristol Stool Score <4): The Bristol Stool Scale categorizes stool into seven grades. As stool shape correlates with retention time in the colon, this score helps assess both intestinal transit time and anastomotic function. Scoring criteria: >5 indicates diarrhea, 6 represents mild diarrhea, and 7 signifies severe diarrhea. (Detailed scoring guidelines are provided in the appendix)

### **Secondary endpoints:**

#### **a. Surgical safety:**

The operation was successful and the treatment effect was accurate, without anastomosis fistula, bleeding, stenosis-related symptoms; no serious complications occurred.

Indicators during operation: operation time, anastomosis time, intraoperative blood loss;

Postoperative indicators: complications within 30 days after surgery and postoperative inflammatory indicators.

Follow-up indicators: anastomosis healing, gastrointestinal iodine water radiography, upper gastrointestinal barium meal, colonoscopy, blood glucose, blood lipid and glycosylated hemoglobin and physiological related indicators.

#### **b. Nutrient metabolism disorder:**

Due to the corresponding nutritional complications such as bile acid malabsorption (BAM) after right hemicolectomy, the patients' albumin level, total protein, VitB12, bile acid and body composition analysis were tested on 3 days, 1 month, 3 months, 6 months and 1 year after surgery.

